## 5.4 Case withdrawal and exfoliation

- (1) All enrolled subjects have the right to withdraw from the study at any time. Reasons for case withdrawal:
  - (2) The subjects asked to withdraw and did not want to continue to participate in the study;
  - (3) Subjects lost follow-up;
  - (4) Participants were deemed unfit to continue in the study for other reasons;
  - (5) The subjects were also participating in other studies.

Subjects who dropped out of the study were considered as shedding cases. When the patient falls off, the patient should be contacted as far as possible, evaluate the project and fill out the research summary page.

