## **3. Study endpoint**

3.1 Primary endpoints: Median overall survival, 3 - and 5-year overall survival rates for the cohort

3.2 Secondary endpoints: overall survival with adjuvant therapy, pancreatic invasion, and advanced tumor

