## **4. Study design**

This retrospective analysis was designed to clarify long-term survival outcomes in patients diagnosed with non-ampulla DA. The study spans a 15-year period, from 2009 to 2023, capturing a comprehensive dataset that reflects advancements in diagnostic and treatment strategies over time. This cohort of 400 patients was carefully selected to provide a robust data set for analyzing survival outcomes and identifying prognostic factors affecting overall survival (OS) and disease-free survival (DFS).

No randomized or any protocol-driven treatment will be administered or provided to the subjects during the study. If clinically applicable, treatment decisions and treatment options are made at the discretion of the treating physician.

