## 6. Study methods and procedures

Because this is an observational retrospective study, no additional visits or laboratory analyses or assessments beyond those required by routine clinical practice are required. Patients must sign the latest Ethic-

approved informed form before performing data collection consent form (ICF), after obtaining the patient's knowledge, the study will collect the patient's clinical routine treatment information.

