#### 6.3 Data source/Data collection process

Data for this study were obtained by extracting routine clinical records of enrolled subjects. The investigator was asked to stay throughout the monitoring period enter information from the original medical record into the study record sheet.

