## **8. Rules to end clinical studies**

The collection ended when 400 non-ampulla DA patients were enrolled.

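### Section 5.4(5) withdraws enrolled patients for taking part in other studies, without rationale or time frame, in a record review that gives no treatment; if they are left out of the analysis, the survival results may be selected

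*Combined protocol and SAP*

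**What the plan says.** Section 5.4 lists reasons for withdrawing an enrolled patient. Item (5) reads: "The subjects were also participating in other studies". On the status of those who leave, the section says: "Subjects who dropped out of the study were considered as shedding cases". It adds only that they should be contacted where possible and a summary page completed.

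The design involves no intervention. Section 4 states: "No randomized or any protocol-driven treatment will be administered or provided to the subjects during the study". Section 6 states: "Because this is an observational retrospective study, no additional visits or laboratory analyses or assessments beyond those required by routine clinical practice are required". Section 6.3 states: "Data for this study were obtained by extracting routine clinical records of enrolled subjects".

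The primary endpoints in section 3 are: "Median overall survival, 3 - and 5-year overall survival rates for the cohort". The secondary endpoints are: "overall survival with adjuvant therapy, pancreatic invasion, and advanced tumor". The statistical text in the synopsis counts OS from diagnosis to death or last follow-up and puts adjuvant therapy in the Cox model.

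Section 8 gives the stopping rule: "The collection ended when 400 non-ampulla DA patients were enrolled".

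Participation in another study does not appear in the inclusion or exclusion criteria, either in sections 5.2 and 5.3 or in the synopsis.

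**The concern.** A bar on taking part in other studies makes sense where a study gives treatment: it protects patients from combined exposures and protects the data from contamination. Neither reason applies to a review of routine records, and the protocol offers no other.

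The rule acts after enrolment, on patients who have met every eligibility criterion, and at a time when survival may already be known. Joining another study can depend on fitness and on receiving systemic treatment. Leaving such patients out would therefore select on something plausibly related both to an exposure under study (adjuvant therapy) and to the outcome. The primary endpoints are meant to describe the cohort, and adjuvant therapy is a secondary endpoint and a Cox covariate, so both could be affected. Section 1 itself warns of possible selection bias in earlier retrospective comparisons of surgery alone with combined treatment; this rule risks adding another source of it.

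**Working it through.** **What the text settles and what it leaves open**

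- Settled: co-participation is a reason for withdrawal (5.4(5)), the study gives no treatment (section 4), and the data come from routine records (sections 6 and 6.3).
- Open, handling: no section says whether a withdrawn patient is excluded, censored at withdrawal, or kept with the data already extracted. No analysis set is defined.
- Open, timing: cases run from 2009 to 2023 (section 4). Consent precedes data collection (section 6), enrolment follows consent (section 6.1), and collection and analysis are planned for April to May 2024 (section 11.4.3). Item (5) could mean participation during that 2024 window or at any time in the 15 years.
- Open, replacement: section 8 says when collection ends, and section 10.1 gives no dropout allowance. Neither says whether withdrawn patients are replaced.

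**The plan's own figure**

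The cohort size of 400 comes with no effect size, power, event count or dropout rate, so there is no calculation to reproduce.

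**Possible size if co-participants are left out**

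The documents give neither the number of co-participants nor their survival. Everything below except the 400 is an assumption.

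Let f be the share of the cohort left out, and d the 5-year OS of co-participants minus that of the others. With all patients, OS = f × S(co) + (1 − f) × S(other). After removal, OS = S(other). The change is therefore −f × d. For the adjuvant group, assume it is 40% of the cohort and contains every co-participant. The share lost from that group is k = f / 0.40, and the change is −k × d.

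| f | Patients left of 400 | Cohort change, d = 0 | d = 10 points | d = 20 points | k | Adjuvant change, d = 10 points | d = 20 points |
|---|---|---|---|---|---|---|---|
| 2% | 392 | 0 | −0.2 | −0.4 | 5% | −0.5 | −1.0 |
| 5% | 380 | 0 | −0.5 | −1.0 | 12.5% | −1.25 | −2.5 |
| 10% | 360 | 0 | −1.0 | −2.0 | 25% | −2.5 | −5.0 |
| 20% | 320 | 0 | −2.0 | −4.0 | 50% | −5.0 | −10.0 |

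Changes are in percentage points of 5-year OS. If co-participants survived less well than the others, d would be negative and every sign would reverse.

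**Two worked cases, 120 adjuvant patients (assumed)**

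- 30 co-participants at 65%, the other 90 at 45%: (30 × 0.65 + 90 × 0.45) / 120 = 0.50, against 0.45 after removal, a change of −5 points. If the remaining 280 of the 400 survive like the non-participants, the cohort change is −(30/400) × 20 = −1.5 points.
- 12 co-participants at 65%, the other 108 at 48%: (12 × 0.65 + 108 × 0.48) / 120 = 0.497, against 0.48, a change of −1.7 points. On the same basis the cohort change is −(12/400) × 17 = −0.5 points.

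**Sampling error for scale**

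The 95% half-width for a proportion of 0.5, ignoring censoring, is 1.96 × √(0.25/400) = 4.9 points at n = 400 and 1.96 × √(0.25/320) = 5.5 points at n = 320. On these assumptions the cohort shift stays below sampling error, and the loss of precision is small.

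**The case against.** The strongest reply is that the plan never says withdrawn patients leave the analysis. Loss to follow-up is on the same list in 5.4, and the OS definition counts to last follow-up, so withdrawal is compatible with keeping the data and censoring. This stands: exclusion is an inference, though a natural one, and the silence would let two analysts draw different cohorts from the same records.

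Second, a reader might infer that anyone who joined a study between 2009 and 2023 is caught. The wording gives no time frame, and the order of consent, enrolment and data collection in 2024 makes concurrent participation a fair reading. A patient whose adjuvant study ended years earlier would then be untouched, and the number affected could be very small.

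Third, a reader might infer from section 8 that withdrawn patients are not replaced and that the analysis must fall below 400. Replacement is simply not addressed.

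Fourth, other studies need not be drug trials. Registry, surgical or observational studies need not select on fitness or adjuvant use. This too stands, and leaves the direction of any effect open.

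Fifth, patients on another study's assigned treatment arguably fall outside a routine-care cohort. The protocol does not give this as its reason, and a sensitivity analysis without these patients would answer it.

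Finally, deleting 5.4(5) leaves investigator discretion in 5.3(4) and 5.4(4), through which the same patients could be removed. That makes deletion alone incomplete, not wrong.

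**Conclusion.** The point holds in conditional form. The protocol contains a post-enrolment withdrawal rule with no stated purpose in a study without intervention, no time frame, and no counterpart in the eligibility criteria. If withdrawn patients are left out, the cohort OS rates and especially the adjuvant-therapy comparison may be selected.

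The documents do not support the stronger statement that trial participants are removed and the results are biased: exclusion from analysis is not stated, the number affected is not given, and a difference in survival is not shown. With no survival difference, the shift is zero. Under the assumed ranges it reaches at most 4.0 points on cohort 5-year OS. For the adjuvant group it runs from 0.5 to 10.0 points, but only with a 10 to 20 point survival difference and with all co-participants in an adjuvant group that makes up 40% of the cohort. The upper ends need 20% co-participation, which is unlikely if only concurrent participation in 2024 counts.

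The change is still worth making: the plan states no benefit from the rule, and removing it costs almost nothing.

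**What to change.** - Delete item (5) from section 5.4.
- State that co-participants stay in all analyses, with the data already extracted and OS counted to death or last follow-up.
- Record co-participation as a yes/no item and report the number of patients affected.
- State that sections 5.4(4) and 5.3(4) are not to be used to remove patients for co-participation.
- Optionally, add a sensitivity analysis without these patients.

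The cost is one deleted line, one data item and a clarifying sentence or two. No patient is affected, because the study does not intervene.

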## 6. Study methods and procedures

Because this is an observational retrospective study, no additional visits or laboratory analyses or assessments beyond those required by routine clinical practice are required. Patients must sign the latest Ethic-

approved informed form before performing data collection consent form (ICF), after obtaining the patient's knowledge, the study will collect the patient's clinical routine treatment information.

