## Summary of research scheme

Program name	Based on long-term survival outcomes of primary non-ampulla duodenal adenocarcinoma
Applicant	Nanfang Hospital of Southern Medical University
Principal investigator	[name]
Study center and director	Southern Medical University Nanfang Hospital [name]
Object of study	Duodenal adenocarcinoma (DA) patients
Objective	
Main Objective: To determine whether radical DA resection is associated with an improvement in 5-year overall survival
 
Secondary objectives: Adjuvant therapy, pancreatic invasion, and advanced tumor stage were identified as significant predictors of overall survival

Study group	Histologically confirmed non-ampulla DA (including all stages of disease at diagnosis)
Study design	Retrospective cohort study
Study duration	2024.04-2024.06
Sample size	400 cases
Inclusion criteria	
(1)At least 18 years old;
 
(2)Voluntary signing of informed consent;
 
(3)Non-ampulla DA patients were diagnosed according to the Chinese Medical Association's Clinical Diagnosis and Treatment Guidelines for Gastrointestinal Tumors (2022 edition), including patients at all stages of diagnosis;
 
(4)Unless there is no other malignant tumor diagnosed in the ampulla DA.

Exclusion criteria	
(1)Cancer of the ampulla or other forms of gastrointestinal cancer
 
(2)Incomplete medical records
 
(3)Missing diagnostic or therapeutic data
 
(4)Follow-up was lost shortly after diagnosis

Efficiency analysis	
Primary outcome measures for effectiveness analysis: median overall survival, 3 - and 5-year overall survival rates in the cohort
 
Secondary outcome measures for effectiveness analysis: Overall survival with adjuvant therapy, pancreatic invasion, and advanced tumor

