## 5.2 Inclusion criteria:

- (1) At least 18 years of age;
- (2) Voluntarily sign informed consent;
- (3) Non-ampulla DA patients were diagnosed according to the Guidelines for Clinical Diagnosis and Treatment of Gastrointestinal Tumors of the Chinese Medical Association (2022 edition), including patients at all stages of diagnosis;
- (4) Unless there are no other malignant tumors in the ampulla other than DA.

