#### 6.1 Informed consent and inclusion

Informed consent (i.e. informed consent signed and dated) is provided. Subjects who meet all other inclusion/exclusion criteria, were considered to be enrolled in this study.

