### **12.2 Informed Consent**

Qualified researchers must explain the nature, purpose, and process of the study in detail to each subject in the informed consent sequence, expected timing, potential risks and benefits, and any discomfort that may arise. Each subject is required to know which the study is voluntary and he/she may withdraw from the study at any time as well as withdraw informed consent without affecting him/her subsequently treatment or relationship with the treating physician.

Informed consent should be given in a standard writing format and in non-professional language as far as possible. Each informed consent form is required, include all of the above and include a voluntary declaration. Informed consent must be submitted to the Ethics Committee for approval.

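### As written, only patients alive to sign consent in 2024 can enter, so overall survival from diagnosis would be strongly overstated

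*Combined protocol and SAP*

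**What the plan says.** The patient's own signature is a condition of entry in several places:

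- Summary, inclusion criterion (2): "Voluntary signing of informed consent". Section 5.2 repeats it: "Voluntarily sign informed consent".
- Section 6: "Patients must sign the latest" ethics-approved form, and this comes before data are collected ("approved informed form before performing data collection consent form (ICF").
- Section 6.1 defines enrolment: "Informed consent (i.e. informed consent signed and dated) is provided", together with the other criteria.
- Section 12.2: "Qualified researchers must explain the nature, purpose, and process of the study in detail to each subject". No relative or representative is named.
- Section 5.4, on patients who drop out: "the patient should be contacted as far as possible".

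The study spans 2009 to 2023 (section 4), and data are collected and analysed in April-May 2024 (section 11.4.3). The consent form goes to the Ethics Committee before the study starts (section 12.1). OS runs from diagnosis to death or last follow-up (summary, statistical analysis). The primary endpoints are median, 3-year and 5-year OS (section 3), and the main objective is the association of radical resection with 5-year OS (section 2). Section 8 sets the stop: "The collection ended when 400 non-ampulla DA patients were enrolled".

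**The concern.** A patient diagnosed in, say, 2012 can sign a 2024 form only if still alive in 2024. All time from diagnosis to signature is then survived by definition, yet it counts as observed survival time. Patients who died earlier, who carry most of the information on survival, cannot enter. The plan describes no delayed-entry (left-truncated) analysis.

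Three things are at stake:

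- **Primary endpoints.** Median, 3-year and 5-year OS are all biased upwards.
- **Main objective.** The group with worse survival loses more patients before consent, so the comparison by resection is distorted.
- **Cox model.** The summary names 11 variables (age, sex, BMI, jaundice, bleeding, anaemia, resection, adjuvant therapy, AJCC stage, differentiation, lymph node involvement rate) plus laboratory values. A cohort of survivors would supply few deaths to fit them.

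**Working it through.** The plan has no figure to reproduce: 400 is stated without power, effect size, expected events or expected survival. The check therefore asks what the written rule would do under stated assumptions.

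**From the documents:** cohort 2009-2023, collection April-May 2024, 400 enrolled, OS from diagnosis, no delayed entry.

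**Inferred:** 2009-2023 is the diagnosis window, and signing takes place in 2024.

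**Assumed:** diagnosis date d uniform on 0-15 years from 1 January 2009; consent at c = 15.25 (1 April 2024); cut-off at e = 15.417 (31 May); true 5-year OS of 20%, 40% or 60%, exponential or with a cure fraction of 15%, 30% or 45%.

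**Formulas**, with S the true survival function:

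- Share alive to sign = (1/15) ∫ S(c − d) dd over 0-15.
- Deaths among 400 = 400 × ∫ [S(c − d) − S(e − d)] dd / ∫ S(c − d) dd.
- Apparent Kaplan-Meier at 5 years = exp(−∫ from 0 to 5 of event density / number at risk), among those alive at c, with time from diagnosis.

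**Worked case**, exponential, true 5-year OS 20%: hazard λ = −ln(0.20)/5 = 0.322 per year.

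- Share alive = (e^(−0.25λ) − e^(−15.25λ))/(15λ) = (0.923 − 0.007)/4.83 = 0.190.
- Deaths = 400 × (1 − e^(−λ/6)) = 400 × 0.0522 = 20.9.

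| Model | True 5-year OS | Alive to sign | Deaths per 400 | Apparent 5-year OS |
|---|---|---|---|---|
| Exponential | 20% | 19.0% | 20.9 | 92.5% |
| Exponential | 40% | 32.5% | 12.0 | 97.2% |
| Exponential | 60% | 49.9% | 6.8 | 98.9% |
| Cure fraction 15% | 20% | 23.7% | 13.2 | 96.0% |
| Cure fraction 30% | 40% | 40.8% | 6.7 | 98.3% |
| Cure fraction 45% | 60% | 58.0% | 3.8 | 99.2% |

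The apparent median is not reached in any row. In the exponential rows, apparent 3-year OS is 95.7%, 98.4% and 99.4%, against a true 38.1%, 57.7% and 73.6%.

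**Sensitivity**

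- Cut-off 30 June: about 6-31 deaths, apparent 5-year OS 89-99%.
- Consent 1 May, cut-off 31 May: about 2-11 deaths, 96-99.6%.
- Records cut at each patient's signature: no deaths, Kaplan-Meier 100% throughout.
- Shorter survival (exponential median 12 months, true 5-year OS 3%): 8% alive, about 44 deaths, apparent 5-year OS about 71%, apparent median about 10 years. With a 30 June cut-off: about 64 deaths, 62% and 7.1 years.

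**Independent simulation**, with consent spread over April-May 2024, a mid-2024 cut-off, a different cure model and true 5-year OS 20-50%: apparent 5-year OS 93-99% and 6-21 deaths per 400. When all diagnosed patients were included whatever their vital status, Kaplan-Meier returned the assumed truth, with 219-330 deaths per 400.

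**Resection comparison** (exponential, 31 May cut-off; naive hazard ratios from a simulated Cox fit with equal numbers diagnosed per group). The true hazard ratio, not resected versus resected, is the ratio of ln S(5); for example ln(0.05)/ln(0.50) = 4.3.

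| True 5-year OS, resected / not | Apparent | True gap → apparent gap (points) | True HR → naive HR |
|---|---|---|---|
| 50% / 5% | 98% / 78% | 45 → 21 | 4.3 → about 14 |
| 60% / 10% | 99% / 86% | 50 → 13 | 4.5 → about 13 |
| 40% / 3% | 97% / 71% | 37 → 26 | 3.8 → about 12 |

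The two scales move in opposite directions. The gap in 5-year OS shrinks because both curves are pushed towards 100%. The hazard ratio grows about threefold because long survivors swell the risk set more in the group with better survival.

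**Events for the Cox model:** 4-21 deaths over 11 named variables is about 0.4 to 1.9 deaths per variable, before any laboratory value is added.

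**The case against.** The strongest reply is that the consent text is template wording not meant literally. The study calls itself retrospective, OS ends at death, survival outcomes are taken from routine records, and sections 4 and 10.1 describe the 400 as already selected. Section 6.4 lists an HCC history, section 11.3 mentions an applicant for drug registration, and section 11.5 mentions SAE reporting; none of these fits this study. On that reading, records of deceased patients would be used and no survivor bias would arise. This may well be the intention, and the bias is therefore stated as conditional. But signed consent is an operative entry criterion in several sections, and section 11.3 forbids departures from the protocol. Either the consent rule is broken or the endpoint is invalid.

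A second reply is that a waiver may stand on pages not available for review. That cannot be excluded. It would remove the bias, but it would still conflict with the requirement in section 6 that patients sign.

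Third, the magnitude rests on assumed survival, accrual and dates. That is true: only the upward direction held in every scenario. It is also fair that percentage-point gaps alone would suggest the resection effect is merely diluted, which is why the hazard ratios are shown beside them. Section 5.4 is weak support on its own, since it concerns patients after enrolment.

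**Conclusion.** The concern holds: the plan is wrong as written and must be fixed. Mandatory signature on the latest form before collection in 2024, applied to a 2009-2023 cohort with OS counted from diagnosis, selects survivors and invalidates the primary endpoints. For an assumed true 5-year OS of 20-60%, only 19-58% of diagnosed patients could sign. Under the base-case dates the overstatement is about 39 points (60% shown as 99%) to 76 points (20% shown as 96%).

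These sizes depend on uniform diagnosis dates, the assumed survival models and the assumed consent and cut-off dates; the direction does not. A delayed-entry analysis would hardly rescue the estimate: with two months from consent to cut-off, 400 patients contribute at most 400 × 2/12 = 67 person-years.

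Confidence is high that the consent text and the endpoints contradict each other. Whether the bias occurs depends on whether the consent text is followed.

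**What to change.** By amendment under section 11.3:

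1. Obtain an ethics-approved waiver of consent for retrospective record review, or another route the committee approves, covering at least deceased and untraceable patients. If one already exists, cite it in section 6.
2. Reword inclusion criterion (2) in the summary and section 5.2, and sections 5.4, 6, 6.1 and 12.2, to match.
3. State that eligible patients from 2009-2023 enter regardless of vital status.
4. Reconcile this with the stop at 400 in section 8, for example by taking all eligible patients or by a selection rule independent of vital status.
5. Report the numbers diagnosed, deceased, approached and included.

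The cost is one ethics amendment and the rewording above, possibly some tracing of vital status, and more abstraction if over 400 patients are eligible and all enter.
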